7.2 Regulatory Considerations

7.2.1 Institutional Review Board/Ethics Committee Approval

As required by local regulations, the Investigator will ensure all legal aspects are covered, and approval of the appropriate regulatory bodies obtained, before study initiation.

Before initiation of the study at each study center, the protocol, the ICF, other written material given to the patients, and any other relevant study documentation will be submitted to the appropriate Ethics Committee. Written approval of the study and all relevant study information must be obtained before the study center can be initiated or the IP is released to the Investigator. Any necessary extensions or renewals of IEC/IRB approval must be obtained for changes to the study, such as amendments to the protocol, the ICF, or other study documentation. The written approval of the IEC/IRB together with the approved ICF must be filed in the study files.

The Investigator will report promptly to the IEC/IRB any new information that may adversely affect the safety of the subjects or the conduct of the study. The Investigator will submit written summaries of the study status to the IEC/IRB as required. On completion of the study, the IEC/IRB will be notified that the study has ended.

Neither the Investigator nor BMS will modify or alter this protocol without the agreement of the other. All agreed protocol amendments will be clearly recorded on a protocol amendment form and will be signed and dated by the original protocol approving signatories. All protocol amendments will be submitted to the relevant institutional IEC/IRB for approval before implementation, as required by local regulations. The only exception will be when the amendment is necessary to eliminate an immediate hazard to the trial participants. In this case, the necessary action will be taken first, with the relevant protocol amendment following shortly thereafter.

Once protocol amendments or consent form modifications are implemented at the lead site, Weill Cornell Medicine, updated documents will be provided to participating sites. Weill Cornell Medicine must approve all consent form changes prior to local IRB submission.

Relevant study documentation will be submitted to the regulatory authorities of the participating countries, according to local/national requirements, for review and approval before the beginning of the study. On completion of the study, the regulatory authorities will be notified that the study has ended.

7.2.2 Ethical Conduct of the Study

The Investigators and all parties involved should conduct this study in adherence to the ethical principles based on the Declaration of Helsinki, GCP, ICH guidelines and the applicable national and local laws and regulatory requirements.

This study will be conducted under a protocol reviewed and approved by the applicable ethics committees and investigations will be undertaken by scientifically and medically qualified persons, where the benefits of the study are in proportion to the risks.

7.2.3 Informed Consent

A co-investigator or qualified designee must obtain documented consent according to ICH-GCP and local regulations, as applicable, from each potential subject or each subject's legally authorized representative prior to participating in the research study. Subjects who agree to participate will receive an oral consent document prior to speaking to a co-investigator.

Informed Consent will occur prior to their pre-test questionnaire, by oral consent for participants until virtual consent methods are approved by the WCM IRB. For oral consent, a member of the study team will review the ICF in-full (see Oral Consent Script attachment) by phone, allowing for questions and reminding the potential subject that participation is voluntary. Oral confirmation of consent to participate will be documented by the study team member.

Once virtual consent processes are established with the JCTO, we will submit an amendment with the IRB to conform to these new policies. We feel that with our older adult population, at a higher risk to COVID-19, that this is best practices in human subjects for participants not to leave their home in order to participate in this study. REDCap consent documents were previous approved in an earlier amendment and we are prepared to use these methods accompanied by a phone discussion as stated above for oral consent.

The initial ICF, any subsequent revised written ICF and any written information provided to the subject must approved by IRB prior to use. The ICF will adhere to IRB/IEC requirements, applicable laws and regulations.

7.2.4 Compliance with Trial Registration and Results Posting Requirements

Under the terms of the Food and Drug Administration Modernization Act (FDAMA) and the Food and Drug Administration Amendments Act (FDAAA), the Sponsor-Investigator of the trial is solely responsible for determining whether the trial and its results are subject to the requirements for submission to <http://www.clinicaltrials.gov>. Information posted will allow subjects to identify potentially appropriate trials for their disease conditions and pursue participation by calling a central contact number for further information on appropriate trial locations and trial site contact information.

7.2.5 Record Retention

Essential documents are those documents that individually and collectively permit evaluation of the study and quality of the data produced. After completion of the study, all documents and data relating to the study will be kept in an orderly manner by the Investigator in a secure studyfile. Essential documents should be retained for 2 years after the final marketing approval in an ICH region or for at least 2 years since the discontinuation of clinical development of the IP. In addition, all subject medical records and other source documentation will be kept for the maximum time permitted by the hospital, institution, or medical practice.

8. Statistical Considerations

Interviews: Interview transcripts will be analyzed according to the constant comparative method, in which new concepts are compared to existing codes (labels that catalog key concepts), existing codes are refined, and a coding structure is developed in stages. This process will continue until theoretical saturation is reached - the point at which no new information is generated from additional interviews.

Pilot testing: statistical considerations. Feasibility will be examined in terms of rates of recruitment and number of sessions completed by participants in the intervention condition. Preliminary analyses to compare the intervention vs. control group on PWD and caregiver sociodemographic characteristics will be carried out in linear models (for continuous variables) and logistic-linear models (for categorical variables). The effectiveness of the intervention will be evaluated in a statistical model that includes treatment (control vs. intervention) and time of assessment (baseline vs. 4 weeks post intervention) as fixed classification factors; the interaction of treatment and time; covariates such as age and gender; and family caregivers (30 per treatment group) as levels of a random classification factor. The primary dependent variable (caregiver contacts primary care practice) is dichotomous, and analysis is by a logistic-linear mixed model with binomial error. Self-efficacy will be included in the model as a fixed classification factor (categorized in 2 levels) as will its interaction with treatment and time. Interactions with other key sociodemographic and clinical variables will also be examined.

9. Adverse Event Reporting Requirements

Adverse event (AE) monitoring and reporting is a routine part of clinical research. Safety is monitored by evaluation of adverse events reported by subjects or observed by investigators or research staff, as well as by other investigations such as clinical laboratory tests, x-rays, electrocardiographs, etc.

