1.1 Study Objectives

1.1.1 Objectives

Objective 1: To develop and refine PICT, an intervention to train family caregivers of PWD how to administer an observational pain assessment tool and communicate the results to health care providers.

Objective 2: To evaluate the feasibility and acceptability of the finalized version of PICT among family caregivers of PWD and health care providers

Objective 3: To test the preliminary efficacy of PICT on 1) caregiver ability to identify pain symptoms; and 2) caregiver efficacy in communicating with health care providers

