1.1.2 Hypotheses / Research Questions

Hypothesis 1: As this study objective involves intervention development only, no hypotheses are given.

Hypothesis 2a (feasibility): 70% or more of participants will meet the benchmark for feasibility, defined by participant retention and adherence to the intervention.

Hypothesis 2b (acceptability): 70% or more of participants will meet the benchmark for acceptability, defined by participant ratings on questionnaires related to “helpfulness,” “future use,” and “overall comprehension” of the intervention content.

Hypothesis 3: PICT will be more effective than an attention control for improving caregivers’ ability to identify pain in PWD and to initiate pain related-communication with health care providers.

2. Background and Significance

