Participants in both conditions will be asked to complete an identical pre-test questionnaire. The questionnaire will be sent to via email or postal mail, and/or will be scheduled to be completed over the phone. We will ask about the participant's background, caregiving role, and comfort speaking with health care providers. It will take approximately 15-20 minutes to complete.

Intervention condition. Participants in the intervention condition will be contacted by a member of the study team to start the PICT workbook. The PICT workbook consists of four sessions and will be completed over the telephone with a study team member. Sessions are conducted once a week and last approximately 30-60 minutes each. Participants will also be asked to read sections of the PICT workbook and complete exercises between sessions. The reading and exercises will take 10-15 minutes to complete. After the final session of the intervention, a study team member will contact the participant by telephone to complete another set of questionnaires (at 12 weeks after the pre-test questionnaire). The questionnaire will be sent to via email, postal mail, or will be scheduled to be completed over the phone. The post-test questionnaires will take approximately 20 minutes to complete and will ask about the participant's comfort and confidence in communicating with health care providers, behaviors he or she observes in the recipient, and views of the PICT workbook. Participants will also be asked to participate in a 20-30 minute telephone interview to elaborate their responses to the questionnaire. Participants must agree to be audiotaped to participate in the study.

Control condition. Caregivers in the control condition will receive an informational pamphlet about pain in dementia and a link to the Alzheimer's Association website. Twelve weeks after the participant completes the pre-test questionnaire, she or he will be contacted by a member of the study team to complete the post-test questionnaire. The questionnaires will be sent via email, postal mail, or will be scheduled to be completed over the phone and will take approximately 20 minutes to complete.

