6.1 Schedule of Assessments

Table 1. Schedule of trial events for interview and field testing phases

	Pre-study	Visit 1 (Interview)
Screening	X	
Informed Consent	X	X
Demographics and Questionnaire		X
Semi-structured Interview		X

Table 2. Schedule of trial events for the pilot test phase

	Pre-study	Week 1	Week 2	Week 3	Week 4	Post-study
Screening	X					
Informed Consent	X					
Demographics and Pre-test Questions		X				
Weekly Session *		X	X	X	X	
In-home reading *		X	X	X	X	
Post-test Questions						X
Exit Interview *						X

* denotes intervention participants only

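### Section 8's natural effect term, treatment-by-time with a free baseline arm difference, is valid but less precise than the same model with a common baseline; the contrast and the timing of self-efficacy need naming (optional)

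*Combined protocol and SAP*

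**What the plan says.** Section 8 (Statistical Considerations) evaluates effectiveness in a single model with treatment, "time of assessment (baseline vs. 4 weeks post intervention) as fixed classification factors; the interaction of treatment and time", covariates of which age and gender are given as examples, and caregivers as a random factor. The outcome is binary: "The primary dependent variable (caregiver contacts primary care practice) is dichotomous". Baseline is therefore one of the two responses, and the treatment main effect leaves the arms free to differ there. Section 8 does not state a common baseline and does not name the contrast that measures the effect.

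Section 8 adds that "Self-efficacy will be included in the model as a fixed classification factor (categorized in 2 levels) as will its interaction with treatment and time". It does not say when self-efficacy is measured.

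Hypothesis 3 (Section 1.1.2) states that "PICT will be more effective than an attention control for improving" the caregiver outcomes. Objective 3 (Section 1.1.1) lists "caregiver efficacy in communicating with health care providers" among those outcomes.

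Section 3.1 says "Participants in both conditions will be asked to complete an identical pre-test questionnaire". Its summary of that questionnaire covers "background, caregiving role, and comfort speaking with health care providers" and does not list contact with the practice. Section 3.1 describes assignment before it describes the pre-test. Table 2 (Section 6.1) puts "Demographics and Pre-test Questions" in Week 1, the same week as the first PICT session. Neither place says whether the pre-test comes before allocation.

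**The concern.** Because Hypothesis 3 speaks of improvement, treatment-by-time is the natural effect term: the change in PICT minus the change in control. Caregivers are randomised, so the expected arm difference at baseline is zero. The planned model estimates that difference anyway and subtracts it in full, so its sampling error enters the effect estimate. In a trial with 50 per arm (Section 3.1) or 30 per arm (Section 8), that can cost a good part of the information on preliminary efficacy.

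A second gap concerns self-efficacy. A post-test value could be changed by PICT if it is the same construct as the efficacy outcome in Objective 3, and adjusting for it could then remove part of the effect. If its interaction with treatment and time is a three-way term, treatment-by-time is also no longer the overall effect unless it is averaged over the self-efficacy levels.

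**Working it through.** **Inputs.** From the documents: two arms, two occasions, binary outcome, caregiver random effect, and 50 per arm (Section 3.1) or 30 per arm (Section 8). The two sizes conflict, so both were run. The documents give no alpha, power, effect size, event rates or correlation, so there is no figure of the plan's own to reproduce. Assumed: two-sided 5% test; contact 35% at baseline in both arms, and 40% (control) vs 62% (PICT) at post-test; no missing data, no covariates and no self-efficacy term.

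**Linear case.** Let s² be the variance at each occasion, rho the pre-post correlation and n the number per arm.

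- Planned treatment-by-time: variance 4s²(1-rho)/n.
- Common baseline: variance 2s²(1-rho²)/n.
- Post-test only: variance 2s²/n.

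Planned / common baseline = 2(1-rho)/(1-rho²) = 2/(1+rho), which is 1.54, 1.33 and 1.18 at rho 0.3, 0.5 and 0.7. It exceeds 1 for every rho below 1. Planned / post-test only = 2(1-rho) = 1.40, 1.00 and 0.60, so below rho 0.5 the planned contrast is less precise than ignoring baseline.

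**Binary case.** Data came from a random-intercept logistic model with intercept SD 0.8, 1.5, 2.5 or 4.0, calibrated to the assumed rates. Likelihood-ratio tests were used, with 8000 simulated trials per setting at 50 per arm and 5000 at 30 per arm. Power (%):

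| Pre-post correlation | Planned, 50 | Common baseline, 50 | Post-test only, 50 | Planned, 30 | Common baseline, 30 | Post-test only, 30 |
|---|---|---|---|---|---|---|
| 0.12 | 37 | 61 | 61 | 26 | 42 | 41 |
| 0.28 | 45 | 64 | 63 | 31 | 44 | 41 |
| 0.47 | 56 | 71 | 63 | 36 | 49 | 40 |
| 0.63 | 68 | 78 | 62 | 46 | 58 | 41 |

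A second method, the noncentral chi-square from the expected likelihood ratio, gives planned vs common baseline of 37/60, 44/63, 54/69 and 66/77% at 50 per arm, and 24/41, 29/43, 36/48 and 45/55% at 30 per arm. The two methods agree within about 3 points. Exact post-test-only power is 62.3% and 41.1%. With no effect (40% in both arms), simulated type I error was 4.7-6.2% for all tests.

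**Source of the gain.** At correlation 0.12-0.28 and 50 per arm, the common baseline gains 19-24 points over the plan but is within 2 points of post-test only. Nearly all of the gain there comes from no longer estimating the baseline difference. Using the baseline value adds clearly only from a correlation of about 0.47.

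**If the arms are not comparable at pre-test (linear case).** The common-baseline estimate is the post-test difference minus rho times the pre-test difference. The planned estimate is the post-test difference minus the whole pre-test difference.

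- Difference d at both occasions, no PICT effect: the common baseline is biased by d - rho·d = (1-rho)d; the planned estimate by d - d = 0.
- Shift d at pre-test only: the common baseline is biased by rho·d in size; the planned estimate by d.

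Binary check by the expected likelihood ratio, 50 per arm, no PICT effect at post-test, SD 0.8 and 1.5. With control at 35% then 40% and PICT at 45% then 50%, the planned test rejects in 5% and 5%, the common-baseline test in 14% and 11.5%. With PICT at 45% then 40%, the planned test rejects in 12% and 14%, the common-baseline test in 5% and 6%.

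**The case against.** The strongest reply is that this is a choice between two valid analyses in a pilot. Section 8 sets no power target, Objective 3 calls efficacy preliminary, and the only numerical benchmarks are for feasibility and acceptability. That stands, and it is why the point is optional.

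The free baseline difference also protects against one real problem. If the arms differ at both occasions, for example through selective loss between allocation and pre-test, the planned contrast is unbiased and the common baseline is not, most of all at low correlation, where the gain is largest. Since the documents do not fix the order of allocation and pre-test, this stands too. A reader might infer that the planned test is the more exposed of the two to a disturbed baseline. That holds only for a shift confined to the pre-test; neither model is uniformly more robust.

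Three further limits stand. Section 8 never names treatment-by-time as the test, so that is a reading. The power figures come from a simplified model without Section 8's covariates or self-efficacy terms. Every rate and correlation is assumed.

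**Conclusion.** The point holds as an optional gain in precision. In the linear case its direction does not depend on the assumptions for any rho below 1; in the binary case the common baseline was more precise in every setting tried. The size does depend on them: about 10 to 24 points of power at 50 per arm under the assumed rates, shrinking as correlation rises. It also requires that contact with the practice is asked at pre-test and that the arms are comparable there.

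A reader might infer that the planned test is biased or that the trial is underpowered. The documents support neither: treatment-by-time is valid under randomisation, and there is no power target to miss. A reader might also infer that the self-efficacy term does remove part of the effect. That would need the post-test value and a shared construct with Objective 3, and Section 8 states neither. If the pre-test value was always meant, this part is only a clarification.

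**What to change.** 1. Confirm that contact with the practice is asked at pre-test, and that the pre-test is completed before the arm is assigned or disclosed.
2. If both hold, keep the logistic mixed model with time, a PICT effect at post-test only, a caregiver random intercept and covariates listed by name. Name the PICT vs control odds ratio at post-test as the primary contrast, and keep the planned free-baseline treatment-by-time model as a sensitivity analysis. State that the odds ratio is specific to this model: under the assumed rates it is 2.8, 3.5, 5.5 and 11.5 at the four correlations, against 2.4 for post-test only.
3. If contact is not asked at pre-test, compare the arms at post-test only. The planned two-occasion model could not be fitted either.
4. Use only pre-test self-efficacy in the model, and put its interactions with treatment and time in a separate exploratory model.

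The cost is a rewording of Section 8, with one model term fewer and no new data if contact is already asked at pre-test. Moderation by self-efficacy becomes explicitly exploratory, and the primary estimate then relies on the arms being comparable at pre-test, which is why the planned model stays as a sensitivity analysis.

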3.1 Overall Design

This study includes the following phases: 1) intervention manual development; 2) Interviews; 3) field-testing; and 4) pilot randomized trial.

Manual development: The Pain Identification and Communication Toolkit (PICT) will be documented in a manual for health care providers and a workbook for caregivers. The provider manual will provide instruction on using the Pain in Advanced Dementia (PAINAD) assessment tool to detect pain in persons with dementia (PWD) and education on specific strategies to promote effective communication between family caregivers and providers, with an emphasis on fostering culturally competent interactions with PWD and their caregivers. The caregiver workbook will include instructions for how to identify pain symptoms using the PAINAD, information on differentiating between pain and dementia symptoms, strategies for effective communication with health care providers, as well as a Question Prompt List (QPL) to help facilitate action planning and culturally appropriate medical visit interactions. A research team comprised of two geriatricians, a geriatric nurse, a gerontologist, and developmental psychologist with extensive experience in conducting research in area of clinical communication will assemble the initial versions of the provider manual and caregiver workbook.

Interviews: As part of the manual development, interviews will be conducted with family caregivers (n=25) and health care providers (n=20) in-person in private offices at WCMC/NYP or over the telephone. The participant, in special circumstances (e.g. scheduling issues) may opt to have the interview take place in a private location convenient to them. All interviews will be recorded and transcribed by a certified, secure, and WCM-approved transcription agency. Participants will be recruited at WCM/NYP locations including the Center on Aging and Weill Cornell Medical Associates. Participants may also be recruited from WCM/NYP geriatric and palliative care support groups. The primary objectives of the interviews are to: a) adapt the PAINAD for use with caregivers by asking them to comment on its format and content; and b) generate an initial question pool for the Question Prompt List (QPL). The secondary objective of elucidating concerns about using a QPL to

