encourage caregivers to ask questions (e.g., increasing visit time) and ways to address those concerns (e.g. instructing caregivers to ask only questions that are of particular concern). The interviews will also address formatting considerations of the caregiver workbook and provider manual (e.g. font size, language that is easy to understand, space for notes). Caregivers will also be asked to fill out a brief questionnaire that will be sent to participants along with the PAINAD tool by email or postal mail, or given to the participant prior to their interview. The questionnaire will include demographics, caregiving role, and patient health questions. Participants will be provided a self-addressed stamped envelope to mail this survey back; or they can use the WCMC secure file transfer to email back the questionnaire.

Field testing. Once initial versions of the PICT manual and workbook are developed, they will be iteratively field-tested and vetted by family caregivers (n=25 per iteration) and health care providers (n=20 per iteration). Participants will be recruited at WCM/NYP locations including the Center on Aging and Weill Cornell Medical Associates. After reviewing the PICT workbook, caregivers will complete a brief questionnaire about the content, format, and perceived utility of PICT, as well as ways to enhance its cultural relevance. They will also complete a brief (15-20 minute) semi-structured interview to clarify their perspectives. Health care providers will answer a similar set of questions. Results from this first field-test will inform the modified version of PICT and will address key issues, such as the feasibility of using research nurses (and other practice staff) to administer the intervention, anticipation of participant burden for caregivers, and adequacy of PICT format and instructions. Study procedures will be repeated (including IRB approval) with a new sample of caregivers (n=25) and providers (n=20). Results from the second field-test will be used to create the finalized intervention of PICT. Prior research indicates that a feasible intervention should be generated after two iterations.

Pilot testing. Family caregivers will be randomly assigned to PICT (n=50) or a control (usual care) condition (n=50).

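### Section 8 does not match the design or Objective 3: arm size and assessment time conflict, the only named outcome is any practice contact, and pain identification has no named measure

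*Combined protocol and SAP*

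**What the plan says.** - **Aims.** Objective 3 (Section 1.1.1) is to test preliminary efficacy on "1) caregiver ability to identify pain symptoms; and 2) caregiver efficacy in communicating with health care providers". Hypothesis 3 (Section 1.1.2) expects PICT to do better than control on "ability to identify pain in PWD and to initiate pain related-communication with health care providers".
- **Design.** Section 3.1, pilot testing: "Family caregivers will be randomly assigned to PICT (n=50) or a control (usual care) condition (n=50". The same section puts the post-test 12 weeks after the pre-test, and says so separately for each arm.
- **Questionnaires.** Section 3.1: "Participants in both conditions will be asked to complete an identical pre-test questionnaire". Its summarised content is "background, caregiving role, and comfort speaking with health care providers". The PICT post-test is said to cover "comfort and confidence in communicating with health care providers, behaviors he or she observes in the recipient, and views of the PICT workbook". For the control post-test only timing, mode and length are given. Section 3.2 lists one common pre-test and a separate post-test for each arm, but the forms are not reproduced.
- **PAINAD.** It appears as teaching content: "The caregiver workbook will include instructions for how to identify pain symptoms using the PAINAD". It is not named as a pilot outcome.
- **Analysis.** Section 8 first describes a general model for effectiveness: treatment, time, their interaction, covariates, and caregivers as a random factor with 30 per group. The two times are baseline and four weeks after the intervention. It then says "The primary dependent variable (caregiver contacts primary care practice) is dichotomous" and assigns a logistic mixed model with binomial error. Self-efficacy enters as a two-level fixed factor that interacts with treatment and time.
- **Schedule.** Table 2 (Section 6.1) puts the pre-test and the first session in week 1 and the fourth session in week 4. The post-test column is labelled as after the study, with no week.

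**The concern.** The analysis section should say how each part of the efficacy hypothesis is measured, when, and on whom. Here it disagrees with the design on when and on whom, and its one named outcome is broader than the communication part of the hypothesis. The other part, pain identification, is left without a measure.

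At stake is how the pilot's efficacy result can be read. An analyst following Section 8 would report an effect on any contact with the practice, over an unstated period, at a time that differs from the one at which the questionnaires are given. The choice of a pain-identification score would fall to whoever analyses the data, possibly after seeing them. A baseline item that was never collected cannot be added afterwards.

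**Working it through.** The documents give no alpha, power, effect size, contact rate or dropout allowance. Neither 30 nor 50 per arm can therefore be reproduced from a sample-size formula. The checks below are for consistency.

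**1. Arm size.** Section 3.1 gives 2 × 50 = 100 and Section 8 gives 2 × 30 = 60, a difference of 40 caregivers. Attrition would have to be 1 − 30/50 = 40% to reconcile them, and no loss allowance is stated. With equal variances, the standard error of a between-arm difference at 30 per arm is √(50/30) = 1.29 times that at 50.

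**2. Assessment time.**
- If the pre-test and session 1 coincide, session 4 falls 3 weeks after the pre-test. Then 3 + 4 = 7 weeks, and 12 − 7 = 5 weeks short of the post-test.
- Counting from week 4 of Table 2, 4 + 4 = week 8, and 12 − 8 = 4 weeks short.
- The two rules agree only if session 1 starts 5 weeks after the pre-test (5 + 3 + 4 = 12). Table 2 does not show that.
- Read instead as the end of a four-week intervention, the time is about week 4, which is also not 12.
- Controls have no sessions, so a time counted from the intervention has no reference date in that arm. Time from the pre-test is defined in both.

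**3. Aims set against the analysis.**

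| Aim | Named outcome in Section 8 | Data described in Section 3.1 |
|---|---|---|
| Pain identification (Objective 3, Hypothesis 3) | None | PICT post-test: observed behaviours, no score named. Pre-test summary: nothing listed |
| Starting pain-related communication (Hypothesis 3) | Any practice contact, yes/no, no counting period | Not listed at pre-test or post-test |
| Communication efficacy (Objective 3) | None; self-efficacy is an explanatory factor only | Comfort at pre-test; comfort and confidence at PICT post-test |

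A treatment-by-time model needs the outcome at both times. The summaries do not show a baseline for contact or for pain identification.

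**4. Why the counting period matters (illustration with assumed rates).** Assume contacts occur at a constant rate r per 4 weeks. Then P(at least one contact in w weeks) = 1 − exp(−r·w/4). The last column is the odds ratio when PICT multiplies the rate by 1.5, that is [exp(1.5·r·w/4) − 1] / [exp(r·w/4) − 1].

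| Assumed r | P at 4 / 8 / 12 weeks | Odds ratio at 4 / 8 / 12 weeks |
|---|---|---|
| 0.25 | 22% / 39% / 53% | 1.60 / 1.72 / 1.86 |
| 0.5 | 39% / 63% / 78% | 1.72 / 2.03 / 2.44 |
| 1.0 | 63% / 86% / 95% | 2.03 / 2.99 / 4.66 |

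For r = 0.5 at 4 weeks: 1 − exp(−0.5) = 0.393, and [exp(0.75) − 1]/[exp(0.5) − 1] = 1.117/0.649 = 1.72. The same effect on the rate thus gives different odds ratios under different windows.

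**5. Self-efficacy.** Section 8 does not say what this covers or when it is measured. If it is communication self-efficacy measured after randomisation, PICT may change it. Conditioning on it could then adjust away part of the effect that Objective 3 seeks.

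**The case against.** The best defence is that Section 8 opens with a general effectiveness model and only then turns to the primary variable. Calling one variable primary leaves room for others, and with a single pre-test and a single post-test any questionnaire outcome would be taken at those times. This stands in part. A reader might infer that pain identification has no model at all and will go untested. The documents do not support that, because the general treatment-by-time structure could be applied to it and the PICT post-test asks about observed behaviours. What is missing is a named score and an error distribution.

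Other stronger readings also fail:
- **That the questionnaires lack the needed items.** Only summaries are available, and the documents do not say that contact is captured by questionnaire. The gap is in what is described.
- **That the counting period changes this trial's primary result.** The rates and the 1.5-fold increase are assumed, and the odds ratios are simple post-test comparisons, not the planned interaction from a mixed model. The effect favours PICT in every row.
- **That non-pain contacts would inflate the effect.** Randomisation balances background contacts in expectation. A spurious rise needs PICT itself to increase contact for other reasons, which nothing in the documents shows. The mismatch with the hypothesis remains.
- **That the trial is underpowered because of the 30.** That figure describes the random factor and feeds no stated power calculation.

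It may also be said that this is a pilot. But Objective 3 and Hypothesis 3 make a comparative efficacy claim, and the contradictions hold whatever the phase.

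**Conclusion.** The point holds and needs correction. Two contradictions are plain on the page: 30 against 50 per arm, and about week 7 to 8 against week 12 for the assessment. The documents do not show which figure is current in either case. The week estimate rests on Table 2's placing of the pre-test and session 1 in the same week.

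Of the two parts of Hypothesis 3, one (pain identification) has no named measure. The other is represented by a yes/no outcome that is wider than the hypothesis and has no counting period. Communication efficacy, as Objective 3 words it, is not a named outcome. The self-efficacy concern is conditional on measurement after randomisation. Confidence is high on the contradictions and the outcome mismatch, and lower on anything that depends on the unseen questionnaires.

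**What to change.** In Section 8, with matching edits to Section 3.1 and Table 2:

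1. Reconcile the arm size and the assessment time. Use one time anchor that exists in both arms, and show the week in Table 2.
2. Define contact as contact about pain, over the same stated look-back period in both arms. Keep the treatment-by-time logistic mixed model only if contact is recorded at baseline; otherwise compare arms at post-test by logistic regression.
3. Name a pain-identification score and the communication comfort/confidence score as efficacy outcomes. Analyse each with a linear version of the plan's own model, or adjust for the pre-test value where it is collected.
4. State which outcome is primary (contact may remain so). Report the others as secondary with 95% confidence intervals.
5. If self-efficacy stays as a factor, say what it measures and use only its baseline value.
6. Check that the outcome items are in the pre-test and in both arms' post-tests.

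The cost is a redraft, a questionnaire check, and possibly a few items added to a pre-test of 15–20 minutes and a post-test of about 20 minutes. If no scored pain-identification measure exists, one must be chosen. No extra participants are needed. The limit is that a missing baseline cannot be recovered for caregivers already past the pre-test; for them the comparison would rest on the post-test.
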